#### **D.4. Develop text prompts and a website-based BI “extender” (Aim 2.b.) [Months 10 – 15]**

**a. Overview.** The BI will enhance motivation using personalized feedback, normative comparisons, female-relevant info, and goal-setting; however, time constraints limit opportunities to address skills. We will use technology to extend the impact of the clinic-delivered BI by developing two complementary intervention extenders: (a) personalized mobile messages and (b) a companion website that can deliver skills training via modeling. The results of this aim will be a text-messaging system and attractive website for use in Aim 3.

**b. Mobile messaging.** Personalized texts will be delivered for 3 months after the BI. Such messages are accepted by young people when they are positive, relevant, and brief. We will craft messages with women’s help (formative work), with words that resonate with them, knowing that texts are “fingered speech” governed by different “rules.” We will use texts to (a) remind women of their self change goals, (b) to inspire and support, and (c) to prompt visits to our website. Each mobile message will end with a link to the website using a URL (unique web address). Texts will be structured with just enough information to intrigue (tease) recipients and drive them to the URL. Texts will be pushed out on a daily basis. Participants do have the option to opt-out of text messages by contacting study staff through the website, by phone, or by email.

**c. Website.** The 2nd extender will be a website – the most flexible/extensible and least expensive type of content repository. It will build upon and broaden the BI. Organization of the web site will be guided by the formative work. Content will target antecedents of alcohol use and sexual behavior, including IMB constructs. For each target, we will include textual, graphic, and (especially) video materials about managing alcohol and sexual risk. Thus, for behavioral skills, we will use high-quality, empirically-validated videos to model intra- (e.g., self-management) and inter-personal (e.g., sexual assertiveness) skills in real world contexts. These videos typically use compelling vignettes, based upon Edutainment principles to model skills and address the barriers and facilitators of skill implementation in the real world. These videos will be accessible, 24/7, to women in their natural environment, eliminating the need for women to find resources on their own. As shown in Table 3, we have already identified empirically-validated source materials that model risk reduction skills; thus, for example, we will extract several skills-based video clips from our professionally produced video (“*Be The Change*”). We will supplement with content that meets the needs identified during our formative work (Aim 1), and identify additional resources already available. We will favor materials that are engaging, female-friendly, and empirically-validated, such as those identified in Table 3. Similarly, to address

| Behavioral Skills                       | Source   |
|--|---|
| Male and female condom use                     | Be The Change 
(R01-MH068171)           |
| Managing substance use to reduce sexual risk   |   |
| Condom use negotiation with a main partner     |   |
| Getting social support for reducing risk       |   |
| Condom use negotiation with new partner        | Safe in the City
(CDC)                               |
| Telling a partner about an STI                 |   |
| How to use a condom and lubricant              |   |
| Standard drinks, BAC estimation                | Rethinking Drinking
(NIAAA)                          |
| Safer drinking strategies                      |   |
| Information (Knowledge)                 |   |
| HIV testing and understanding test results     | What Do You Know
About HIV Testing
(R21-NR011997) |
| STIs and STI testing                           | Safer Sex Resources
(Planned Parenthood)             |
| Safer Sex options                              |   |
| Definitions of low-risk and high-risk drinking | Rethinking Drinking                                     |
| Motivation                              |   |
| Importance of using condoms with every partner | Be The Change 
(R01-MH068171)           |
| Testimonials of HIV-infected women             |   |

information and motivation, we will extract video segments and provide links to patient-oriented and interactive science-based websites (see Table 3) to present information about reducing alcohol use and sexual risk.

Once materials are assembled, we will work closely with our university web designer to follow best practices in health-related website design; we will build an easy-to-navigate website tailored to women’s needs. We will draw upon our previous health communications research (R01-MH068171) to make the website highly appealing, intuitive, and informative. We expect to engage women using interactive FAQs and Q&As, and to develop a chat interface that allows women to ask questions (cf. “Go Ask Alice”) that will be answered by our team. These plans will be

elaborated and strengthened based on our formative work.

**d. Pilot Testing of Technology.** Pilot testing of the technology will be added to the pilot testing of the BI described in D.3.d. To pilot test the technology a password protected website has been created based on information learned through our formative research (Aim 1). Participants will be shown this website and be guided through an “over-the-shoulder test” which includes tasks designed to test how well a participant can maneuver through the website as well as their thoughts on content and design (See Aim 2 Over the shoulder Protocol). Half of the participant recruited in Aim 2 will receive BI and then over the shoulder technology testing and half will receive the reverse order. Pilot testing of the technology may be omitted if we reach saturation.

#### **D.5. Randomized Control Trial of the BI, Messaging, and Website Extenders (Aim 3) [Months 13 – 24]**

**a. Overview.** We plan a pilot study to assess the feasibility and acceptability of the BI and website, to obtain preliminary evidence of BI efficacy (on alcohol use and sex behavior outcomes), and to determine feasibility of procedures (e.g., enrollment, BI and website exposure, follow-up rates) for a future RCT.

**b. Design.** We plan a 2 (interventions) x 2 (baseline, follow-up) design. Women will be randomized, complete baseline, receive intervention (BI or brochure), post-survey (BI arm only), and 3-month follow-up. Measures will assess IMB constructs, alcohol, and sexual behavior, and STIs. Rationale for control: We chose a brochure because it is a science-based (CDC and NIAAA material) alternative that is representative of what clinics currently provide.

**c. Sample** ( $n=50$ ) was based on published guidelines for treatment development research, which recommend 15-30 per cell for Phase IB research. This also aligns with NIH expectations for R34 research. We recognize that the trial is not adequately powered to detect between-group differences, but it can clarify the potential of the intervention and suggest effect sizes (ES). We also know that ES estimates will have large standard errors. We primarily aim to find a pattern of results that is supportive of the experimental treatment.

**d. Participants.** We will recruit 50 women using screening, eligibility, recruitment, and consent procedures described in D.1.c. Women who participated in Aim 1 or 2 will not be eligible.

**e. Baseline.** Participants will complete the CASI on a tablet computer. Measures included in the CASI are listed in Table 2; the measures are reliable and valid, and have been used in prior research with young women. The CASI will take ~45 mins, and will assess background variables, outcomes, mediators, and moderators.

The self-report **outcomes** include sexual behavior; alcohol use; and the co-occurrence of sex and alcohol.

Consistent with PA-13-078, we will assess hypothesized **mediators** and **moderators**. We recognize that we will not have sufficient statistical power to test mediation or moderation in this pilot. However, we will evaluate short-term intervention effects on the hypothesized intervening variables, to determine if they have promise as potential mediators for a subsequent RCT.

Potential **mediators** include IMB constructs: (a) information, (b) motivation, and (c) skills. To assess information we will use knowledge questionnaires. To assess motivation, we will use measures of norms, attitudes, and behavioral intentions towards alcohol use, condom use, and partner concurrency. Importantly, we will assess condom use norms and intentions by partner type; we will also assess norms, attitudes and intentions towards partner concurrency, rarely done in prior intervention studies. To assess behavioral skills for condom use we will use a measure of condom use problems and assess self-efficacy by partner.

Potential **moderators** include demographic (e.g., age, race); sexual history (e.g., number of partners, STI diagnoses, prior victimization); mental health (depression and anxiety; assessed with PHQ-9 and GAD-7); drug use (DHQ).

**f. Intervention.** Women randomized to the **control condition** will receive (after the baseline CASI) a Fact Sheet on Alcohol Use and Risks to Women’s Health prepared by the CDC. This details gender differences in alcohol intoxication, facts about alcohol use and reproductive health, pregnancy, and other women’s health concerns. Control women will then be scheduled for their follow-up session.

Women randomized to the **BI** will receive a ~45 min BI (as detailed in Table 1 and Aim 2) delivered by a health educator. After the BI, participants will be told that they will receive daily mobile messages with health facts of the day for 3 months. Women will be encouraged to visit and use the website. At the end of the BI session, women will complete a post-BI satisfaction survey, be scheduled for the follow-up. For all women, at the end of the session, the RA will thank the participant and reimburse her \$30 for completing the CASI.

**g. Process measures.** We will assess the **fidelity** with which health educators implement the **BI** by reviewing session content against a content checklist based on the manual that to obtain a % adherence score; and using blind ratings that identify behaviors consistent with MI spirit (e.g., empathetic engagement,

eliciting concerns and solutions from patients, collaborative focusing, goal setting) and skills (e.g., open questions, reflective listening, affirmations, summarizing). These process data will be used in supervision and to refine the interventionist training protocol for the R01. We will evaluate the patients' perceptions of the degree to which the interventionist maintained MI style using the Client Evaluation of Counseling scale.

Website use metrics (e.g., URL access, dates, frequency, videos watched, pages viewed) will determine which participants accessed the site, temporal effects of the text prompts, and the patterns of content viewing.

**h. Follow-up measures.** Three months after baseline, women will return to the clinic for a CASI (see Table 2 for content) as well as a semi-structured qualitative interview. The qualitative interview will be audiotaped. Audio will be uploaded to a secure Lifespan database following the interview. Once study staff have listened to the interview and completed a written debrief and possible transcription the audio will be destroyed. The qualitative interview will consist of open ended questions about the study appointments. Women in the BI condition will complete additional items to rate the website and messaging content quality and appeal, ease of use, and relevance; and respond to open-ended prompts that elicit suggestions for message and website improvement. For all women, at the end of the session, the RA will thank the participant and reimburse her \$40. If a participant is unable to return to the clinic for the three month follow-up then the follow-up can be conducted remotely. The participant will be sent a link via email to complete the computerized survey. The participant will be called on the telephone to complete the qualitative interview. Participants will be issued a check for reimbursement for remote follow-ups.

With patients' permission, we will review medical records for STI incidence data (to prepare for subsequent RCT). This follow-up will allow us to refine the procedures for an RCT, establish feasibility of follow-up sessions, and provide preliminary evidence of short-term outcomes.

**i. Data analysis.** This is a R34 pilot; thus, analyses are not powered to detect treatment effects. We will inspect means and percentages to assess feasibility and acceptability and to obtain preliminary evidence of efficacy.

To determine **feasibility** of the BI and of an RCT, we will calculate the percentage of individuals who were: eligible; consented; attended their intervention; accessed the website; and returned for the follow-up. Based on previous research, we expect  $\geq 90\%$  of those assigned to a BI to attend their intervention. Based on our recent trials (R01-MH068171), we expect  $\geq 80\%$  of all women to return for the 3-month follow-up.

To determine **acceptability** of the BI, messaging and website, we will calculate Ms for the satisfaction surveys, and inspect responses. We **predict** that the intervention materials will be well-accepted, as shown by mean ratings  $\geq 4$  on a 5-point Likert scale. To further evaluate the **acceptability** of the messaging and website, we will collect use metrics (e.g., timing and frequency of website access, number of clicks on links for information, video view time). We **predict**, and will construe as acceptable, if women receive messages, link to the website, and view videos all the way through/multiple times.

To obtain preliminary evidence of BI **efficacy**, repeated measures ANOVAs will test intervention and time effects on the primary outcomes (alcohol use frequency, quantity, binge frequency; condom use, number of sexual partners; alcohol use before sex). We **hypothesize** an intervention x time interaction for all outcomes; thus, we **hypothesize** that BI recipients but not controls will reduce alcohol use and alcohol use before sex, increase proportion of protected sex, reduce condom use problems and number of partners.

To prepare for a future trial, we also provide preliminary data on mechanisms of action by testing intervention effects on **hypothesized mediators** (e.g., IMB constructs, attitudes, norms, self-efficacy).

**j. Effect sizes and power.** We recognize that effect size estimates based on small samples often have large SDs and wide confidence intervals (CIs). We also acknowledge that we will not have power to detect statistically significant results. Nonetheless, pilot data are useful to gauge whether BI effects are encouraging, to examine distribution of outcome variables, to inform future analytic approaches, and to suggest the range of effect sizes that are reasonable to expect in a future trial. Thus, the focus of our analyses will not be on strict significance testing but on estimating effect sizes and CIs.

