**Aim 2:** Patients will be told that there is a study about a new service designed to help women to reduce STI risk, that the study involves completing four possible parts: a computerized survey, meeting with a counselor and receiving feedback about their health behaviors, providing feedback about the session, and providing feedback about the developed technology. Women will be told that the consultation is free, and that they will be invited to provide feedback on the experience. In exchange, they will be compensated \$40. Interested patients will hear about study procedures, provide verbal informed consent, and schedule a session.

**Aim 3:** Patients will be told that study participation will involve two health behavior assessments separated by 3 months; in addition, participants will be assigned (randomly) to receive standard services supplemented by (a) an educational brochure detailing the effects of alcohol on sexual risk and women's health (control) or (b) a meeting with a health educator that includes receipt of feedback about their health behaviors as well as technology extenders to be used in between the two assessments. Women in both conditions will receive \$30 for completing the baseline assessment and \$40 for completing the follow-up assessment.

**All Aims:** After procedures are described, women will be asked questions to ensure comprehension. For Aim 1 and Aim 2 those who show understanding and interest will be scheduled for a focus group (Aim 1) or intervention (Aim 2). For Aim 3 those who show understanding and interest will sign a consent form and be scheduled for an assessment. Contact information will be obtained for reminder calls/texts as well as contact information for two "locators" who will be contacted in the event that the participant is unreachable.

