| 
 
generate a written personalized plan for reducing risk and discuss strategies to achieve goals; offer menu of options that includes strategies articulated by focus-group women
 
                           | 
 
Generate SMART goals: specific, measurable, achievable, realistic, and time-targeted
 
Discussion of protective strategies may enhance skills and support self-efficacy
 
Written plan allows for later review and reminders
 
 |
| 
 
discuss role of texts as reminders; mention that 3mo follow-up will be an opportunity to assess how she is doing with regard to her goals
 
   | 
 
Encourage commitment language; prompt public commitment to change and accountability
 
   |

**d. Pilot testing.** Screening, recruitment, and consent will occur as described in D.1.c. We will recruit ~8-15 women who will provide information about alcohol use, consequences, and sexual behavior, including partner-specific risk history using a computer-assisted self-interview (CASI). Measures of alcohol use and sexual behavior sample a 3-month interval to optimize reliability and representativeness. As seen in Table 2, we will assess alcohol use and problems, sexual behavior, and client satisfaction. The sexual measures will reflect risk as a function of relationship type. Given the prevalence of hookups and serial monogamy, we will assess start and end dates to measure the gap interval between relationships. This assessment will allow us to tailor risk reduction strategies in the integrated BI, and afford a fine-grained approach to determining BI efficacy. The computer will score the items immediately, and generate personalized feedback (i.e., risk summary, plan) for use by the interventionist during the BI.

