**Table 2. Constructs and Measures (How data will be used, research aim, and time of administration)**

| Construct                            | Measure   | Use     | # items | Aim 2  |    | Aim 3 |    | Aim 2 / 3 |
|--------------------------------------|---|---------|---------|--------|----|-------|----|-----------|
|                                      |   |         |         | Screen | BL | BL    | 3M | Post      |
| Demographics                  | Age, Ethnicity, Race, Marital status, Education, Employment, SES, Living Arrangements, Gender/Gender Identity, Reason for visit, Health Insurance   | D, M    | 13      | x      |    | x     | x  |           |
| Alcohol Use                   | Heavy drinking frequency/quantity   | S, F, O | 2       | x      | x  | x     | x  |           |
|                                      | Drinks/week, quantity/frequency, maximum quantity   | F, O    | 4       |        | x  | x     | x  |           |
|                                      | Alcohol quantity before sex   | F, O    | 2       |        | x  | x     | x  |           |
| Alcohol problems              | SIP-2R  | F, O    | 26      |        | x  | x     | x  |           |
| Alcohol Protective Strategies | Positive alcohol behavioral strategies, Consumption self-control, Stopping/Limit setting, Harm reduction  | F       | 22      |        | x  | x     | x  |           |
| Sexual behavior               | Sex risk: (a) sex >1 partner, (b) sex with someone who had other partners, (c) did not use a condom every time                                      | S       | 7       | x      |    |       |    |           |
|                                      | Pregnancy attitudes and intentions  | D       | 9       |        | x  | x     | x  |           |
|                                      | Sex History: Lifetime partner #, Past 3 months partner #, Condom Use past 3 months, alcohol with sex past 3 months, # HIV-positive partners         | D, O    | 13      |        | x  | x     | x  |           |
|                                      | Partners: (a) #, (b) relationship type(s), (c) condom use, (d) involving alcohol, (e) partner STI testing, (f) monogamy, (g) trust, (h) risk of STI | D, F, O | 7xP     |        | x  | x     | x  |           |
|                                      | Sex-Related Alcohol Expectancies  | M       | 13      |        |    | x     | x  |           |

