| Mental health                 | Depression / Anxiety (PHQ-9; GAD-7)   | S, M    | 17      | x      |    | x     | x  |           |
| Life Stress                   | Perceived Stress Scale  | D       | 4       | x      |    |       |    |           |
|                                      | Social Readjustment Rating Scale  | D, M    | 42      |        |    |       | x  |           |
| Drug use                      | Drug history Questionnaire (DHQ)  | D, M    | 14      | x      |    | x     | x  |           |
| Victimization                 | Revised Sexual Experiences Survey   | D, M    | 12      |        |    | x     | x  |           |

|                     |   |      |    |   |   |   |   |   |
|---------------------|---|------|----|---|---|---|---|---|
|                     | Childhood Sexual Abuse                                  | D, M | 3  |   |   | x |   |   |
|                     | Intimate Partner Violence (HITS)                        | D, M | 5  |   |   | x | x |   |
| Literacy     | Single Item Literacy Screener                           | S    | 1  | x |   |   |   |   |
| BI process   | Client Evaluation of Counseling scale                   | M    | 16 |   |   |   |   | x |
| Satisfaction | Brief intervention and website                          | O    | 5  |   | x |   |   | x |
| Web use      | Hits, return hits, # pages viewed (collected by server) | O, M |    |   |   |   |   | x |

How data will be used: S = screen, F = feedback, D = descriptive, O = outcome, M = potential mediator / moderator. P = # of partners.

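### The protocol randomizes women before the self-reported baseline survey and does not say that the arm stays hidden until the survey is submitted; a low-severity point with a very cheap fix.

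*Protocol*

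**What the plan says.** Protocol D.5.b sets the sequence for Aim 3: "Women will be randomized, complete baseline, receive intervention (BI or brochure), post-survey (BI arm only), and 3-month follow-up". This is the only statement in the supplied text of when randomization happens relative to the baseline survey. D.5.e makes that survey a self-completed tablet CASI, which supplies the self-reported alcohol and sexual behavior outcomes.

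At consent (D.1.d) every woman hears about both arms, and the BI arm is described as "a meeting with a health educator that includes receipt of feedback about their health behaviors". For Aim 2, D.3.d explains where the feedback comes from: "The computer will score the items immediately, and generate personalized feedback". D.5.f carries that session into the trial as a "BI (as detailed in Table 1 and Aim 2) delivered by a health educator".

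The key to Table 2 reads "How data will be used: S = screen, F = feedback, D = descriptive, O = outcome". The row "Drinks/week, quantity/frequency, maximum quantity" is coded F and O, and so are heavy drinking, alcohol quantity before sex, and the SIP-2R consequences scale. Number of partners appears in two rows: Partners, which carries F, and Sex History, which is coded D and O only.

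The SAP fits GEE models with time (baseline and follow-up), condition and their interaction, adjusted for age. Before that, it uses t-tests and chi-square tests, including on the outcome measures, to judge whether randomization gave equivalent groups.

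**The concern.** A woman who knows she is about to discuss her answers with a health educator may report her drinking differently from one who expects a brochure. If the arm were known before the CASI, baseline could shift in one arm only. Baseline is not merely descriptive here. It is one of the two time points in the interaction, so the shift would pass straight into the estimated effect. The same holds for the repeated measures ANOVA in protocol D.5.i.

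D.5.c and D.5.j make effect sizes and confidence intervals a main product of the pilot, to inform the next trial. A biased estimate would therefore be carried forward.

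The baseline comparison also changes meaning. In the stated order it uses outcome data collected after randomization, so it cannot separate chance imbalance from a reporting shift.

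**Working it through.** The plan gives no figure to reproduce on this point. The check has two parts: what the text settles, and how much a shift could matter.

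**What the text settles**
- Order: randomization, then baseline, then intervention (D.5.b).
- Disclosure: D.5.f gives the control fact sheet after the CASI. That times the handing over of the material, not the revealing of the arm, and it fits either reading.
- Blinding: the only blinding stated is of the fidelity ratings (D.5.g). The only masking is of the inclusion criteria in the screening survey (D.1.c).
- Feedback link: clear for drinks per week, maximum quantity, heavy drinking and SIP-2R. It also holds for alcohol before sex if, as the SAP's description of a count of drinks suggests, the alcohol-quantity row was used. It is open for number of partners, because the SAP does not say which Table 2 row supplied the count.

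**Size of a possible shift (hypothetical inputs; the documents give none)**

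Assume control means of 1.0 at both times and BI means of 1.0 then 0.80. Let b be the proportional reporting shift at baseline in the BI arm and f the shift at follow-up.

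1. Count outcomes (Poisson, log link assumed). Interaction ratio = 0.80(1+f)/(1+b).
   - b = -0.10, f = 0: 0.80/0.90 = 0.89.
   - b = +0.10, f = 0: 0.80/1.10 = 0.73.
   - b = f = -0.10: 0.72/0.90 = 0.80. An equal shift at both times cancels.
2. Alcohol consequences (linear model). Difference in change = 0.80(1+f) - (1+b) - 0, against a true -0.20 of the baseline mean.
   - b = -0.10, f = 0: 0.80 - 0.90 = -0.10.
   - b = +0.10, f = 0: 0.80 - 1.10 = -0.30.
   - b = f = -0.10: 0.72 - 0.90 = -0.18.

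Under-reporting at baseline in the BI arm pulls the interaction toward no effect; over-reporting exaggerates it. No figure is offered for condomless sex, which the SAP analyzes with a zero-inflated model.

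**Set against the pilot's imprecision**

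With n women per arm (n = 25 if 50 are split 1:1, which is assumed), coefficient of variation CV, and within-woman correlation 0.5 (assumed), SE of the log ratio = sqrt[2 × CV²/n × (2 - 2 × 0.5)].

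| n per arm | CV | SE | 95% CI for 0.80 |
|---|---|---|---|
| 25 | 0.5 | 0.141 | 0.61 to 1.06 |
| 25 | 1.0 | 0.283 | 0.46 to 1.39 |
| 20 (80% retention, D.5.i) | 0.5 | 0.158 | 0.59 to 1.09 |
| 20 (80% retention, D.5.i) | 1.0 | 0.316 | 0.43 to 1.49 |

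The 10% under-report moves the log ratio by -ln(0.90) = 0.105. At 25 per arm that is 0.105/0.141 = 0.75 SE or 0.105/0.283 = 0.37 SE.

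**The baseline test as a safeguard**

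A 10% shift equals 0.10/CV standard deviations: 0.20 SD at CV 0.5 and 0.10 SD at CV 1.0. A two-sided 5% t-test with 25 per arm has power of about 11% and 6% for these. It needs 0.81 SD for 80% power, so a non-significant result would not rule out a modest shift.

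**The case against.** The strongest reply is that the harm is conditional at every step. The woman must learn her arm before the CASI, that must change her answers, and the change must differ by arm. A reader might infer from the order in D.5.b that women knew their arm when they completed baseline. The documents do not support that. D.5.b is one summary sentence, the timing of the fact sheet in D.5.f fits disclosure after the CASI, and the consent pages, where the sequence might be explained, are not in the supplied text. This objection stands, and it limits the point to a possible bias.

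A reader might also infer that every primary outcome feeds the BI feedback. That goes too far for number of partners, given the Sex History row without F.

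The SAP drops non-significant interactions, and one might count the effect on the remaining condition term as further damage. In the example that term averages the two times, (1.0 + 0.80)/2 = 0.90, with no reporting shift at all. That dilution comes from dropping the interaction, not from the order of randomization, so it is not counted here.

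Finally, the 10% shift has no source in the documents, and the protocol already warns of wide intervals. Both are true. They make the point small, but imprecision is no reason to keep a bias that a sentence can remove.

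**Conclusion.** The point holds as a cheap improvement of low severity. The stated order puts randomization before a self-reported baseline that the efficacy model uses as a time point, and no supplied text says that the arm is withheld until the CASI is submitted. If the arm was concealed until then, nothing was lost.

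If it was not, a 10% shift in one arm would move a ratio of 0.80 to 0.89 or 0.73, which is less than one standard error under the assumptions above. The direction would depend on whether BI women under- or over-reported. These figures rest on the assumed means, shift, CV, correlation, log link and 1:1 allocation. Separately, in the stated order the baseline outcome comparison cannot serve as a check of randomization alone.

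**What to change.** Change D.5.b so that the baseline CASI is completed before the arm is revealed. There are two ways:

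- **Keep the early draw but conceal it** from the woman and the research assistant until the CASI is submitted. This leaves unchanged the denominator of the 90% attendance target, which D.5.i sets among women "of those assigned to a BI to attend their intervention".
- **Randomize after the CASI**, and report losses between consent and CASI beside that target. This changes the denominator. With 25 assigned to the BI and three lost before baseline, attendance is at most 22/25 = 88% in the stated order, but could be 22/22 = 100% if only women who completed the CASI were randomized.

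The SAP is written in the past tense. If the data are already collected, report the actual sequence, when the arm was disclosed, and losses before baseline by arm in the CONSORT figure. Do not present the baseline outcome comparison as a check of randomization alone, and carry the revised order into the next trial.

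The cost is one or two sentences in the protocol and one in the SAP, with no added visits or measures; a health educator must be available before the arm is known. For a completed trial the cost is reporting only.

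The change does not deal with arm-specific reporting at follow-up. That is also plausible, because Table 1 has BI women told that the "3mo follow-up will be an opportunity to assess how she is doing with regard to her goals".
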